2.5.8 Procedures to assess safety

Safety assessments for dermal tolerability such as erythema, inflammation and ulceration will be made by investigators. Adverse events will be documented and analyze.

2.5.9 Schedule of study visits

	Randomized Phase												Open-Label Phase				
	Day 0	Day 1	Week 1	Week 2	Month 1	Week 6	Month 2	Week 10	Month 3	Week 14	Month 4 ^a	Baseline ^b	Month 1	Month 2	Month 3	Month 4	
	Clinic Visit		Phone Call										Phone Call				
Medical History	X	X	X	X	X		X		X		X	X	X	X	X	X	
Adverse Events		X	X	X	X		X		X		X	X	X	X	X	X	
Vital Signs	X	X															
Direct Skin examination	X	X															
IGA grading			X		X		X		X		X	X	X	X	X	X	
Wound selection and randomization	X												X ^c				
Application of matrix in clinic	X	X															
Application of matrix at home			X	X	X	X	X	X	X			X	X	X	X	X	
Wound culture	X						X				X						
Itch and pain scores	X		X	X	X	X	X	X	X	X	X	X	X	X	X	X	
Caregiver survey									X		X						
Wound size measurements	X	X	X		X		X		X		X	X	X	X	X	X	
Photographs by investigator	X	X															
Photographs at home			X		X	X	X	X	X	X	X	X	X	X	X	X	

Study timeline:

Randomized Phase:

Day 0: in person visit; randomization of wounds with wound photography, application of matrix and monitoring of adverse events (matrix application within 30 days of screening).

Day 1: in person assessment of wounds.

Day 2 (optional): review of wounds with photographs.

Telehealth assessment at **Week 1, Week 2, Month 1, Month 2, Month 3 and Month 4** (a window of ± 7 days for the monthly scheduled visits is expected).

Participant will provide pain and itch surveys and photographs every two weeks.

Additional visits (over secure video platform or phone calls), and reapplication of matrix by caregiver may be scheduled if deemed necessary.

Open-Label Phase:

Baseline Open-Label: telehealth assessment; selection of wounds and baseline wound photography, application of matrix and monitoring of adverse events.

Telehealth assessment at **Open-Label Month 1, Open-Label Month 2, Open Label Month 3 and Open-Label Month 4** (a window of ± 7 days for the monthly scheduled visits is expected). Participant will provide pain and itch surveys and photographs at every Open-Label Month visit. Participants can reapply up to once a week. Additional visits (over secure video platform or phone calls), and reapplication of matrix by caregiver may be scheduled if deemed necessary.

a The **Baseline Open-Label** visit could be done during the **Randomized Phase Month 4**.

b The **Baseline Open-Label** visit could be done up to two weeks after the **Randomized Phase Month 4** visit.

c During the **Baseline Open-Label** visits the investigator will select the wounds to be treated during the Open-Label Phase. No randomization will be required.

2.6 Study outcome evaluations

2.6.1 Study endpoints

Primary endpoint:

Comparison of the duration of wound closure (weeks) of matrix treated wounds vs control wounds from baseline to Month 4. Wound photos will be captured bi-weekly by caregivers.

Secondary endpoints:

1. Comparison of application site adverse events (burning, erythema, pain) between matrix treated wounds vs control wounds after application;
2. Comparison of wound pain (Wong-Baker FACES scale) between matrix treated wounds vs control wounds at month 1, month 2, month 3, month 4 (prior to matrix application);
3. Comparison of wound itch (Itch NRS/Itchy Man scale) between matrix treated wounds vs control wounds at month 1, month 2, month 3, month 4 (prior to matrix application);
4. Comparison of wounds that reach >50% healing from baseline in matrix vs control wounds at month 1, 2, 3, 4;
5. Comparison of wounds that reach >70% healing from baseline in matrix vs control wounds at month 1, 2, 3, 4.

Exploratory endpoints:

1. Comparison of caregiver responses on wound dressing ease of use on matrix treated wounds vs control wounds with the Caregiver Global Impression of Change (CrGI);
2. Comparison of change in wound cultures between matrix treated wounds vs control wounds at Month 2 and Month 4,

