PRIMARY OBJECTIVE	
To assess the preliminary efficacy of matrix treatment in RDEB wound
 
To assess safety profile of matrix treatment in RDEB wound

SECONDARY OBJECTIVES	To assess improvement in wound pain with matrix treatment in RDEB wound To assess improvement in wound itch with matrix treatment in RDEB wound To assess caregiver responses on wound dressing ease of use with matrix treated wounds To compare the change in wound cultures between matrix treated wounds vs control wounds
NUMBER OF SUBJECTS	6-10 subjects for enrollment of at least 20 wound pairs
SUBJECT SELECTION CRITERIA	
Inclusion Criteria: Clinical and/or genetic diagnosis of RDEB by a dermatologist, age 6 years or older willing and able to give consent/assent and have at least 6 wounds (3 wound pairs) each with an area of 10cm² or greater located at any site (excluding face and genital skin). The first patient that will be enrolled is an adult patient before the recruitment of pediatric patients. Wounds must be present for at least 4 weeks and able to be classified as recurrent wounds (wounds that heal within 12 weeks but then re-blister) vs chronic open (older than 12 weeks).
 
Exclusion Criteria: Actively infected wounds with pus (colonized wounds are eligible), areas that have had squamous cell carcinoma (SCC), areas on the face and genitals, and areas that have been treated with investigational therapies in the past 3 months.

INVESTIGATIONAL DEVICE / INTENDED USE	Spincare The Spincare matrix is delivered from a portable, hand-held device that produces an electrospun healing matrix made of biocompatible materials that attaches directly to the wound bed.
CONTROL GROUP OR OTHER STUDY ARMS (if applicable)	Standard of care non-adhesive wound dressings and bandage changes currently used.
DURATION OF SUBJECT PARTICIPATION AND DURATION OF STUDY	Subjects will be on study for up to 4 months Screening: performed over phone and then virtually (up to 30 days before Day 0 treatment day) Treatment: 1-3 days (subjects to attend clinic) Follow-up: 4 months Open-Label Phase: 4 months The total duration of the study is expected to be 1 year. 4 months for subject recruitment and 6 months for final subject follow-up is anticipated.

CONCOMMITANT MEDICATIONS	Allowed: current EB medications (i.e., pain meds, vitamins, iron infusions, antibiotic ointments, oral antibiotics if needed). Prohibited: none

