STATISTICS Primary Analysis Plan	
Sample size calculation: We calculated that a sample size of 40 wounds (20 matrix-treated vs 20 untreated) would give us 90% power to detect a difference of 8.5 vs 6 weeks (SD=3) of wound closure duration between matrix treated vs untreated wounds with a two-sided alpha of 0.05.
 
Recruitment plan: We will recruit our cohort of 6-10 patients from various settings including the Stanford EB clinic (~100 RDEB patients), our clinical research database (75 RDEB patients), and the Epidermolysis Bullosa Clinical Research Consortium (EBCRC) (290 RDEB patients). Many of these patients have already received a clinical and/or genetic diagnosis of RDEB and have detailed medical and wound histories recorded

Rationale for Number of Subjects	This sample size calculation is based on our prior natural history study of 720 RDEB wounds for 6 months in 13 RDEB adult and pediatric participants. We anticipate that the majority of pediatric wounds will be the recurrent type. If the Spincare matrix decreases the duration of wound closure, then this clinical trial would show a novel wound healing device that may improve wound closure duration in difficult to heal RDEB wounds. We would assess the secondary endpoints to determine if a 2.5 week longer wound closure is clinically meaningful and associated with wound specific decreases in pain and itch.

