2.6.2 Sample size determination

We calculated that a sample size of 40 wounds (20 matrix-treated vs 20 untreated) would give us 90% power to detect a difference of 8.5 vs 6 weeks (SD=3) of wound closure duration between untreated vs matrix treated wounds respectively a two-sided alpha of 0.05. This sample size calculation is based on our prior natural history study of 720 RDEB wounds for 6 months in 13 RDEB adult and pediatric participants. We anticipate that the majority of pediatric wounds will be the recurrent type. If the Spincare matrix reduces the duration of wound closure, then this clinical trial would show a novel wound healing device that may improve wound closure duration in difficult to heal RDEB wounds. We would assess the secondary endpoints to determine if a 2.5-week shorter wound closure is clinically meaningful and associated with wound specific decreases in pain and itch.

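### The primary endpoint is sized as a difference in weeks, but the plan has no rule for wounds not more than 90% closed by Month 4, and it defines the endpoint in two opposite directions

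*Combined protocol and SAP*

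**What the plan says.** Section 2.6.1 gives the primary endpoint as "Comparison of the duration of wound closure (weeks) of matrix treated wounds vs control wounds from baseline to Month 4". Section 2.5.7 has the investigator judge closure (more than 90% healing) from photographs every two weeks for 16 weeks.

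The endpoint's direction differs between two places:

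- **Section 2.6.2** plans for "a difference of 8.5 vs 6 weeks (SD=3) of wound closure duration between untreated vs matrix treated wounds". Matrix is at 6 weeks, and the effect is described this way: "We would assess the secondary endpoints to determine if a 2.5-week shorter wound closure is clinically meaningful". Shorter is better, which is time to closure.
- **The synopsis** uses the same two figures in the other order, "between matrix treated vs untreated wounds with a two-sided alpha of 0.05", which puts matrix at 8.5 weeks. It adds: "We would assess the secondary endpoints to determine if a 2.5 week longer wound closure is clinically meaningful". Longer is better, which is weeks spent closed. The same synopsis row also speaks of the matrix decreasing the duration, so it is not consistent with itself.

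The synopsis requires wounds to be classifiable as "recurrent wounds (wounds that heal within 12 weeks but then re-blister) vs chronic open (older than 12 weeks"), and the criteria in sections 2.4.3 and 2.4.4 do not exclude the chronic type. Section 2.6.3 anticipates that more wounds will pass 90% closure with matrix.

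On analysis, section 2.5.7 states an intention-to-treat aim and section 3.3 repeats it for withdrawn subjects. No test, model, censoring rule or value for an open wound is given. Section 2.3.1 notes that closure sometimes cannot be read while the matrix is intact.

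**The concern.** The planning inputs (two values in weeks and an SD) are those of a comparison of means. Such a comparison needs a number of weeks for every randomised wound. If the endpoint is time to first closure, a wound still open at Week 16 does not supply one. The analyst must then drop it, assign it a value, or change method, and the plan does not say which.

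The choice matters. Dropping open wounds conditions on the outcome, contradicts the intention-to-treat aim, and removes from view the effect section 2.6.3 anticipates, namely more wounds closing. Assigning Week 16 changes both the difference and the SD behind the sample size. The trial is unblinded (section 2.5.4), so a rule chosen after the photographs have been read would leave the primary result open to challenge.

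**Working it through.** **Inputs from the documents.** 20 wounds per arm, 8.5 versus 6 weeks, SD 3, two-sided alpha 0.05, stated power 90% (section 2.6.2); readings every two weeks to Week 16 (section 2.5.7). The documents give no closure rate, no overall share of chronic wounds and no within-pair correlation. Every non-closure share below is an assumption.

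**1. The plan's own figure.** Standardised difference = 2.5/3 = 0.833. A two-sample t-test with 20 per arm has power 73% (75% by the normal approximation). The stated 90% is not reproduced on this basis. That shortfall is a separate matter; 73% is simply the starting point here.

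**2. How many open wounds do the inputs allow?** If control times are normal with mean 8.5 and SD 3:

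- P(open at Week 16) = P(Z > (16 − 8.5)/3) = P(Z > 2.5) = 0.6%.
- For matrix, P(Z > (16 − 6)/3) = P(Z > 3.33) = 0.04%.

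Under normality the calculation leaves almost no room for unclosed wounds.

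**3. Dropping open wounds can reverse the direction.** Constructed example: in each arm 50% of wounds close at a mean of Week 6, matrix closes a further 30% at a mean of Week 12, and the rest stay open.

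| | Matrix | Control |
|---|---|---|
| Share closed | 80% | 50% |
| Closers-only mean | (0.5×6 + 0.3×12)/0.8 = 8.25 | 6.0 |
| Restricted mean to Week 16 | 0.5×6 + 0.3×12 + 0.2×16 = 9.8 | 0.5×6 + 0.5×16 = 11.0 |

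Among closers the device looks 2.25 weeks slower. With all wounds kept it is 1.2 weeks faster.

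**4. Dropping open wounds hides an effect on the share closing.** Simulation with 20 independent wounds per arm and the same timing among closers (mean 7, SD 3):

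| Unclosed, control vs matrix | Closers-only t-test rejects | Rank test, open wounds placed last, rejects |
|---|---|---|
| 40% vs 20% | about 5% | about 20% |
| 50% vs 20% | about 5% | about 38% |

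A 5% rejection rate is the type I error rate, so the closers-only test has no power for this effect.

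**5. Setting open wounds to 16 weeks.** Assume that 8.5, 6 and SD 3 describe closers only, that a share u never closes in either arm, and that arms are independent. Then

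- difference = 2.5(1 − u);
- variance in an arm with closer mean m = 9(1 − u) + u(1 − u)(16 − m)².

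For u = 0.1, control variance is 8.1 + 0.09×56.25 = 13.16 and matrix variance is 8.1 + 0.09×100 = 17.10. The pooled SD is √15.13 = 3.9.

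| u | Difference (weeks) | Pooled SD | Power (t-test) |
|---|---|---|---|
| 0 | 2.50 | 3.0 | 73% |
| 10% | 2.25 | 3.9 | 43% |
| 20% | 2.00 | 4.4 | 28% |
| 30% | 1.75 | 4.8 | 20% |
| 40% | 1.50 | 4.9 | 16% |

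**The case against.** Several points against the concern carry weight.

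- **The endpoint may not be time to closure.** A reader might infer that never-closed wounds have no value at all. On the synopsis reading, weeks spent closed, such a wound scores 0. The lack of a value is therefore confined to the section 2.6.2 reading. What remains on the synopsis reading is that the zero score is unwritten and that a cluster at 0 sits poorly with SD 3.
- **No test is named.** A reader might infer that the plan has chosen a flawed comparison of means. The documents do not say so; the comparison is implied by the sample size inputs only.
- **A mean and SD do not fix a tail.** The 0.6% needs normality. The one-sided Chebyshev bound allows up to 9/(9 + 7.5²) = 13.8% of control wounds at or beyond Week 16.
- **The inputs may already include open wounds.** They come from a natural history study of 720 wounds, and its handling of unclosed wounds is not described. If so, the power loss in step 5 is overstated. Step 5 also ignores the matching in section 2.5.3.
- **Closers-only runs against the stated intent.** Intention to treat argues against dropping wounds, and the example in step 3 was built to show a reversal. But intention to treat assigns no number to an open wound, so it does not close the gap.
- **How common non-closure will be is unknown.** No rate is given, and section 2.6.2 expects most pediatric wounds to be recurrent. It is tempting to say that many wounds will stay open. The documents support only that some should be expected.

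**Conclusion.** The concern holds in a conditional form, with medium confidence. The plan gives no way to include wounds not more than 90% closed by Month 4, although it admits chronic open wounds and anticipates a difference between arms in the number closing. It also states the endpoint in opposite directions, and that conflict has to be resolved before any rule can be written.

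On the time-to-closure reading, a comparison of weeks cannot be computed for every randomised wound, and the closers-only version can miss or reverse the effect. The fall in power from 73% to 43–16% is a sensitivity range. It rests on assumed non-closure of 10–40%, equal in both arms, on planning inputs that describe closers only, and on independent arms. It is not an estimate of this trial's power.

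**What to change.** 1. Reconcile the synopsis with section 2.6.2 and define the endpoint as either time to first closure of more than 90% or total weeks spent closed.
2. Keep every randomised wound in the primary analysis.
3. If the endpoint is time to closure, prespecify one analysis. An example is restricted mean time to closure through Week 16, with never-closed wounds administratively censored at Week 16, closure treated as falling between consecutive two-weekly readings, and standard errors that respect wound pairs and patients.
4. Write a rule for readings blocked by an intact matrix. These arise only in treated wounds, so censoring at the last readable photograph would differ by arm and could be informative. Treat closure as interval-censored up to the next readable assessment, and add a sensitivity analysis.
5. If the endpoint is weeks spent closed, state that never-closed wounds score 0.
6. State the assumed share of wounds never closing and whether the natural history inputs already include such wounds. Then restate the power.

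The cost is SAP wording. The same photographs are used. The restated power may well be less favourable than 90%.

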2.3.1 General study design

Pilot study in 6-10 subjects where wounds will be randomized 1:1 to matrix or no treatment (control): Patients will be asked to review and sign the informed consent form. The matrix will be applied to randomized treatment wounds (computer generated randomization), along with a non-adhesive bandage as a protective layer. At the time of matrix application, the investigator will score amount of wound burning, pain, or other adverse events. Non-treated wounds will have the patient's standard of care, and the non-adhesive bandage applied. Reapplication of matrix treatment may be required soon after the initial application depending on how well the matrix has propagated with the first application. Subjects and caregivers will be trained on how to take photos. We will ensure that photos of the face are NOT included to protect patients' confidentiality. One day after a wound examination will be performed in clinic. The investigator will assess the adherence of the matrix, and any adverse events (AEs).

Thereafter a caregiver may travel to the participants home to apply the matrix device to randomized, treated wounds once a month or more frequently if required (up to once-a-week application is allowed, the patient will record when they have applied the matrix treatment at home and the reason). Spray application(s) may be skipped at the discretion of the PI to address any concerns or adverse events. Investigators will perform remote monitoring (via phone call or virtual platform) at Week 1, Week 2, Month 1, Month 2, Month 3 and Month 4 (additional interim visits may be required) to assess for adverse events and track progress. Additional photographs will be taken, and investigators will use Telehealth to monitor for healing and safety reporting. Compliance is verified by bi-weekly photographs. Wound swabs of treated and untreated wounds will be taken prior to spray treatment and at Month 2 and Month 4. After Month 1, patients are given the option to not put any dressings on their wounds if this is medically acceptable and in line with the patient preference. Throughout the visit wound closure assessments may not be always possible if the Spincare matrix is still intact and this will be indicated on the source document. No Spincare treatment is to be applied 2 weeks prior to the end of the visit to allow for wound size measurement.

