2.3.2 Study design schematic

2.4 Subject selection

2.4.1 General characteristics of the proposed subject population(s)

Patients aged 6-65 years old with a clinical and/or genetic diagnosis of recessive dystrophic epidermolysis bullosa. This target population was chosen as they suffer from large painful wounds usually resistant to conventional treatment and would benefit the most from matrix treatment with the Spincare device.

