2.4.3 Inclusion criteria

1. Subject has a clinical and/or genetic diagnosis of RDEB by a dermatologist;
2. Subject is age 6 years or older willing and able to give consent/assent;
3. Subject has at least 6 wounds (3 wound pairs) each with an area of 10cm² or greater located at any site (excluding face and genital skin);
4. Subject wounds must be present for at least 4 weeks.

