2.5.2 Study treatment or diagnostic product procedures

The Spincare device produces a wound dressing matrix that is sprayed to the wound bed. It uses a laser system to help with correct distance position to produce a uniform matrix that is electrospun to the wound bed. The device is currently available in Israel and 11 European countries but is not FDA-approved or cleared on any indications. In the current literature the main indications are acute and chronic wounds, partial thickness burns and ulcers and the matrix treatment has been used in more than 20 countries so far. A case study of Spincare treatment in EB has been described.

A full body wound examination will be performed by the investigator and target wound areas will be identified. All eligible wound sites will be randomized for matrix treatment versus standard of care wound dressings (6 wounds, or 3 wound pairs). The matrix will be applied to randomized treatment wounds, along with a non-adhesive bandage (e.g. Telfa, Mepitel, Rylon, etc.) as a protective layer. At the time of matrix application, the investigator will ask about any potential wound burning sensations, pain, or other adverse events. Non-treated wounds will have the patient's standard of care and non-adhesive bandage applied. Subjects and caregivers will be trained on how to take photos. Wound pain and itch are captured at least every 2 weeks.

The matrix treatment will be applied on Day 0 in clinic. Day 1 visit will be mandatory to assess for any adverse events (Day 2 is optional and may be required particularly if AEs have occurred and this will be at the discretion of the

PI). Subsequent applications will be performed by a caregiver if needed up to once a week.

Detailed Schedule:

Randomized phase:

Day 0 – Spincare would be applied to wounds after randomization process and covered with a non-adhesive dressing. Reapplication of matrix treatment may be required depending on how well the matrix has adhered with the first application. The need for this will be assessed by the investigators.

Day 1 – A wound examination will be performed in clinic one day after the initial application. The investigator will assess the adherence of the matrix, and any adverse events (AEs).

Day 2 is optional and may be required if medically indicated at the discretion of the PI.

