Week 1, Week 2, and Months 1, 2, 3, 4 – Investigators will arrange telehealth assessment at Week 1, Week 2, Month 1, Month 2, Month 3 and Month 4 (additional interim phone call visits/telehealth assessment at **Week 6, Week 10 and Week 14**, or more frequently, if deemed necessary). A caregiver may travel to the participants home to apply the matrix device to randomized, treated wounds (up to once a week if needed, they will record the date of application and the reason). Additional photographs will be taken, and investigators will use Telehealth to monitor for healing and safety reporting. At the time of matrix application, the caregiver will score amount of wound burning, pain, or other adverse events. Matrix will not be applied after **Week 14** to ensure the final wound assessment at Month 4.

Month 4 – Telehealth (End of Randomized Phase) Visit: The investigator will virtually assess wound healing compared to baseline photographs in the treated and control wounds. Digital photographs of the treatment and control wounds will be taken with a ruler by the caregiver/participant and sent to the investigator. All wound photos will be stored and reviewed on the REDCap. The participant's preference to enroll on the Open-Label Phase will be assessed.

Open-Label Phase:

Participants who are eligible for the Open-Label Phase, at the discretion of the investigators (taking into consideration participant's prior documented adverse events, current medical status, and adherence to trial protocol), and who choose to participate, will be provided with the Spincare matrix and will be instructed to apply it once a week at most. Participant will be allowed to treat previously randomized wounds (treated and control wounds) and new wounds, up to a max of 10 individual wounds; there won't be control nor randomized wounds. The wounds would be selected at the Open-Label Baseline remote visit and will need to meet the same wound criteria as the Randomized phase. At minimum during each monthly visit, participants will be required to provide digital photos taken with a ruler before and after the application of the Spincare matrix. Additionally, they will complete surveys regarding their pain and itch, offer updates on their

medical history, provide information about concurrent medications, and report any adverse events. No blood draws, wound cultures and in person visits will be required during the Open-Label phase.

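### The application-site safety endpoint has no same-wound reference before application, and its scoring is tied to an application that control wounds do not receive

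*Combined protocol and SAP*

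**What the plan says.** Section 2.6.1 gives secondary endpoint 1 as "Comparison of application site adverse events (burning, erythema, pain) between matrix treated wounds vs control wounds after application", and the synopsis has the same line. Neither place gives a reference state, a grade, a time window or a counting unit. In the same list, endpoints 2 and 3 (pain, itch) are fixed at monthly times before matrix application, and endpoints 4 and 5 (healing) are measured from baseline.

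On capture at application:
- Section 2.3.1: at matrix application in clinic, "the investigator will score amount of wound burning, pain, or other adverse events".
- Section 2.5.2, Day 0 procedures: "the investigator will ask about any potential wound burning sensations, pain, or other adverse events", so here the signs are asked about and not scored.
- Section 2.5.2, visits from Week 1 on: "At the time of matrix application, the caregiver will score amount of wound burning, pain, or other adverse events".
- Section 2.5.8: "Safety assessments for dermal tolerability such as erythema, inflammation and ulceration will be made by investigators". No grading scale is named.

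On the wounds at entry, section 2.4.1 says of the patients that "they suffer from large painful wounds usually resistant to conventional treatment". Section 2.4.3 requires an area of at least 10 cm² and adds: "Subject wounds must be present for at least 4 weeks".

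Section 3.2.1 defines an unanticipated adverse device effect, association with the device and seriousness. It does not define an ordinary adverse event as new or worsened.

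The schedule in section 2.5.9 marks itch and pain scores on Day 0, not on Day 1, and again from Week 1. Adverse events, direct skin examination and investigator photographs are marked on Day 1. The examination and photographs are also marked on Day 0. No burning score has a row.

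**The concern.** Safety is part of the primary objective (section 1.3.1), and irritation with burning, pain and itch is the first anticipated risk (section 3.1). Endpoint 1 is the endpoint that compares local tolerability between randomized wounds.

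A wound that was painful before the matrix went on may still be painful afterwards. Unless each wound is compared with its own earlier state, such a wound can be recorded as having an application-site event in either arm. The plan does not rule this out, and it leaves the investigator and each caregiver to choose a rule in an unblinded study (section 2.5.4).

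The control side has a second gap. Burning and pain are scored when matrix is applied. Control wounds get no matrix, so the plan does not say when, or whether, they are scored for the same signs on the same occasions. They do have pain scores in the regular schedule, but these are not placed around an application, and burning has none.

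At stake are the size of the difference that the pilot reports and the meaning of the event rate in matrix wounds. The independent monitoring review of adverse-event results before pediatric enrolment (section 5.0) would see the same data.

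**Working it through.** **Plan's own figure.** There is none for this endpoint: no event rate, test or power is stated. The 90% power in section 2.6.2 concerns closure duration and is not an input here.

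**What exists before and after the first application**

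| Sign | Before application, Day 0 | Day 1 | Control wounds |
|---|---|---|---|
| Pain | Score on Day 0, not timed relative to application | No score; adverse events only | Scheduled pain scores, none tied to application |
| Burning | None listed | Adverse events only | No scoring occasion stated |
| Erythema | Examination and photographs on Day 0, ungraded | Examination and photographs | The plan does not limit these to treated wounds |

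A reference could therefore be built for erythema, and for pain if the Day 0 score is taken first. None can be built for burning.

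**Size if signs already present are counted.** Inputs:
- b = share of wounds showing the sign before application (not in the documents; shown from 0 to 90%)
- q = 30% new onset in matrix wounds (assumed)
- c = 5% new onset in control wounds (assumed)
- 20 pairs (the synopsis asks for at least 20 wound pairs)

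Formulas for a yes/no sign:
- matrix rate = b + (1 − b)q
- control rate = b + (1 − b)c
- difference = (1 − b)(q − c)

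At b = 50%: matrix 0.50 + 0.50 × 0.30 = 65%; control 0.50 + 0.50 × 0.05 = 52.5%; difference 0.50 × 25 = 12.5 points. The share of matrix-wound events that are pre-existing is 0.50 / 0.65 = 77%.

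| b | Matrix | Control | Difference | Exact McNemar power, 20 pairs |
|---|---|---|---|---|
| 0 | 30% | 5% | 25 points | 34% |
| 50% | 65% | 52.5% | 12.5 points | 7% |
| 70% | 79% | 71.5% | 7.5 points | 4% |
| 90% | 93% | 90.5% | 2.5 points | 0.3% |

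Power is for a two-sided 0.05 test, with the two wounds of a pair independent and pairs independent of each other. The plan names no test; McNemar is used because the wounds are matched.

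**Sensitivity**
- Stronger effect, 50% vs 5%: power falls from 86% (b = 0) to 20% (b = 50%) and 8% (b = 70%).
- Pre-existing signs fully shared within pairs, 30% vs 5%: power is 4% at b = 50% and 0.5% at b = 70%.

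The difference keeps its sign in every row, because (1 − b) is never negative.

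**The case against.** A reader might infer that the protocol counts any burning, erythema or pain present after application, so that the event rate is mostly disease and the matrix effect is hidden. The documents do not support that:

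- No section says that signs merely present are counted. The rule is missing. Adverse event can be read as new or worse, section 3.1 describes irritation that arises when the matrix is applied, and sections 3.2.3 and 3.2.5 require a causality assessment. This stands against any claim that the plan states a wrong rule. It does not fill the gap: causality is judged event by event, without blinding, and gives no common threshold for recording an event.
- Wounds are randomized within patient and matched on size, severity and location (section 2.5.3). Pre-existing signs should be about equally frequent in both arms, so the consequence is dilution and not a reversal. This stands.
- The dilution formula assumes a yes/no sign. Section 2.3.1 scores an amount, which can rise in a wound that already hurts. A comparison of amounts between randomized wounds does not shrink by (1 − b), apart from a ceiling on the scale. This stands, so the table is conditional. The endpoint, however, is worded as events, and no rule converts an amount into an event.
- Only prior pain is documented. Prior erythema and burning are not stated, and the synopsis calls only one of its two wound classes open. This stands.
- Day 1 is not empty: adverse events, skin examination and photographs are scheduled. Only the itch and pain row is blank.
- Power is low even with a clean definition, and this is a pilot. This stands; the case for the change rests on an interpretable comparison more than on power.

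**Conclusion.** The point holds in a conditional form. Endpoint 1 has no same-wound reference, and the plan schedules neither a burning score before application nor a matching score in control wounds. This goes beyond wording, because a burning baseline that was never collected cannot be reconstructed at analysis.

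If signs already present are counted, the difference is diluted by the share of wounds already affected: from 25 points to 12.5 at a share of one half, under assumed new-onset rates of 30% vs 5%. The raw matrix-arm rate could not then be attributed to the matrix. The direction of the comparison is not at risk from this source. The true share is not in the documents, and the size rests on that share, on the assumed rates and on a yes/no count. The change should be made; it does not call the design into question.

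**What to change.** 1. Define an application-site event in secondary endpoint 1 (section 2.6.1 and synopsis) as burning, erythema or pain that is new or worse than the same wound's state before the Day 0 application.
2. Score pain and burning before the Day 0 application and again at Day 1, in both wounds of each pair and at the same times.
3. Take erythema from the Day 0 and Day 1 examinations and photographs already scheduled, read for both wounds.
4. Compare within pairs.
5. Make sections 2.3.1 and 2.5.2 agree on whether the investigator scores these signs or only asks about them.

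The cost is a few extra CRF fields at two clinic visits that already take place. Treatment, visit dates and sample size do not change. Power for this endpoint remains modest: about 34% with 20 pairs under the assumed 30% vs 5%, and that figure takes worsening to be as easy to detect in a wound already affected as onset is in one that is not. The result should be reported as an estimate, and a non-significant difference should not be read as evidence of tolerability.
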